2.1 Objectives

The primary objective of this clinical investigation is to demonstrate that the MPP feature is effective by converting a percentage of CRT non-responders to responders. Each subject's responder status will be assessed using a Clinical Composite Score (CCS) including three components: NYHA Class, heart failure (HF) hospitalizations, and cardiovascular death (Packer et al., 2001).

The MPP sub-study also includes three secondary endpoints.

2.1.1 Primary Endpoint 1

The purpose of primary endpoint 1 is to evaluate the CRT responder status with the MPP feature within the Ilivia 7 HF-T QP family CRT-D or Acticor/Rivacor 7 HF-T QP family CRT-D system, compared to a pre-specified performance goal.

The associated hypothesis is evaluated based on a CCS determining a responder classification based on changes in NYHA class, HF hospitalization, and cardiovascular death.

A responder status will be derived classifying these subjects as "Improved", "Worsened", or "Unchanged" using the following definitions.

Responder Classification at the 6-Month MPP Follow-up (evaluated compared to MPP enrollment visit):

- "Improved":
 - No HF hospitalization or cardiovascular death, AND
 - NYHA class is improved
- "Unchanged":
 - No HF hospitalization or cardiovascular death, AND
 - NYHA class is unchanged
- "Worsened":
 - HF hospitalization or cardiovascular death has occurred, OR
 - NYHA class is worsened

Ho: The proportion of subjects (P) who are classified as "Improved" is not superior to a performance goal (PG) of 3%.

$$PG \geq P$$

Ha: The proportion of subjects who are classified as "Improved" is superior to a performance goal of 3%.

$$PG < P$$

A rejection of the null hypothesis would indicate that the proportion of subjects classified as “Improved” is superior to 3%.

2.1.2 Secondary Endpoint 1

The purpose of Secondary Endpoint 1 is to evaluate adverse events that require additional invasive intervention to resolve, specifically related to the MPP feature of the Ilivia or Acticor/Rivacor HF-T QP family. These adverse events include any software issues related to MPP programming or any adverse event that occurs while MPP is enabled and that may be attributed to the use of the MPP feature.

2.1.3 Secondary Endpoint 2

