The purpose of Secondary Endpoint 2 is to evaluate a modified CCS, determining a responder classification based on changes in NYHA class, Patient Global Assessment (PGA), HF hospitalization, and cardiovascular death, where the PGA will ask subjects to assess how their overall status has changed since prior to receiving CRT therapy (markedly better, better, unchanged, worse, markedly worse).

Modified Responder Classification (CCS + PGA) at the 6-Month MPP Follow-Up (evaluated compared to MPP enrollment visit):

- “Improved”:
 - No HF hospitalization or cardiovascular death, AND
 - Neither NYHA class is worsened or PGA is worsened (“worse” or “markedly worse”), AND
 - NYHA class is improved or PGA is improved (“better” or “markedly better”)
- “Unchanged”:
 - No HF hospitalization or cardiovascular death, AND
 - NYHA class is unchanged, AND
 - PGA is unchanged (“unchanged”)
- “Worsened”:
 - HF hospitalization or cardiovascular death has occurred, OR
 - NYHA class is worsened or PGA is worsened (“worse” or “markedly worse”)

2.1.4 Secondary Endpoint 3

The purpose of Secondary Endpoint 3 is to evaluate the Responder Classification (as defined in Section 2.1.1) in which both “Improved” and “Unchanged” subjects will be classified as responders. At the time of enrollment into the MPP sub-study, MPP sub-study subjects have already been found to have no change or worsening in their HF status with BiV pacing. Since HF is a chronic and progressive condition,

these subjects may be expected to continue to worsen during the MPP follow-up period or remain stable with careful management. In this secondary endpoint, a status of “Unchanged” (in addition to “Improved”) during the MPP follow-up period will be considered a responder to MPP.

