2.2 Subject Status Definitions

The subject status definitions utilized in this study are provided in Table 3.

Table 3: Subject Status Definitions

Subject Status	Definition
Provisionally enrolled	
Subject has provided written informed consent but has not yet been screened against the MPP sub-study specific inclusion and exclusion criteria.
 
Provisionally enrolled subjects will become fully enrolled if they meet the MPP sub-study specific inclusion and exclusion criteria, and complete the MPP Enrollment visit.
 
Provisionally enrolled subjects will not be included in the analysis population for the study objectives; however, they may be included in analysis of additional data of interest.

Screen Failure	
Subject has signed consent, but at the time of consent it was identified the subject does not meet all inclusion/exclusion criteria,
 
OR
 
Subject consented prior to implant, but prior to implant the subject status changes.
 
Subject will be exited and will not be included in the analysis population or count toward the enrollment maximum.

Fully Enrolled	
Subject meets all of the MPP sub-study specific inclusion criteria and none of the exclusion criteria, and completes the MPP Enrollment visit.
 
Fully enrolled subjects will be included in the analysis population for the study objectives, as well as in the analysis of the additional data of interest.

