2.6.1 Replacement of Missing Data

The last observation carried forward (LOCF) principle will be utilized for the analysis of NYHA Classification and Patient Global Assessment for primary endpoint 1 and secondary endpoints 2 and 3.

Missing NYHA and patient global assessment data at either the enrollment or follow-up visits affects the number of subjects that can be included in the analysis. It is possible that subjects or study personnel may either forget or choose not to answer one or more of the questions related to NYHA classification or patient global assessment.

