2.6.2 MPP Sub-Study Analysis Population

The primary and secondary endpoint analyses will be conducted according to the intention-to-treat principle (ITT) utilizing all available data from fully enrolled subjects. Subjects are expected to remain programmed with the MPP feature ON from MPP enrollment through the completion of the sub-study. Subjects who have the MPP feature permanently turned OFF prior to completion of the sub-study will be required to report a protocol violation; however, these subjects will be included in the analysis population. All available data from subjects that undergo a pulse generator change and no longer have an MPP eligible device will be included in the analysis. Subjects may have the MPP feature temporarily turned OFF due to a lead revision procedure and these short durations with MPP will not be reported as a protocol violation.

Any QP ExCELS subject that does not enroll into the MPP sub-study but receives MPP due to the physician's determination will not be analyzed towards the MPP study endpoints.

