3.4.3 Date of Study Termination

The expected study termination for all subjects should not be earlier than the 6 month follow-up visit.

For all early study terminations, the following rules apply:

- In case of withdrawal of consent, date of study termination is the date of withdrawal of consent.
- In case of subject death, the date of study termination is the date of death.
- If subject is lost to follow-up, date of termination is the date of last documented contact with the subject.
- If BIOTRONIK Ilivia 7 HF-T QP family CRT-D system or Acticor/Rivacor HF-T QP family CRT-D system and/or Sentus QP LV lead was not implanted, the date of termination is the date of decision not to implant.
- If prior to MPP enrollment, the BIOTRONIK Ilivia 7 HF-T QP family CRT-D system or Acticor/Rivacor HF-T QP family CRT-D system and/or Sentus QP LV lead was explanted and not replaced with an MPP sub-study eligible system, the date of study termination is the date of system revision.

Study related procedures and documentation should end at the day of study termination for the respective subject.

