5.1.1 Clinical Events Committee – MPP Sub-Study Events

The QP ExCELS Clinical Events Committee (CEC) described in Section 5.1 will adjudicate all adverse events that require additional invasive intervention to resolve which may be related to the MPP feature. These events include any software issues related to MPP programming or any adverse event that occurs while MPP is enabled and that may be attributed to the use of the MPP feature. The CEC will indicate whether the adverse event is related, possibly related, not related, or has an unknown relation to the MPP feature.

In addition, the CEC will adjudicate all deaths reported while participating in the MPP sub-study and classify each death as cardiovascular, vascular, non-cardiovascular/vascular, or unknown.

The CEC will adjudicate all reported protocol-defined hospitalizations while a subject is enrolled in the MPP sub-study. Hospitalization events will be classified as cardiovascular, vascular, non-cardiovascular/vascular, or unknown. Additionally, hospitalizations classified as cardiovascular will be further classified as a HF hospitalization, non-HF hospitalization, or unknown. Hospitalization events reported by the investigator as part of the initial responder classification for enrollment into the MPP sub-study will not be adjudicated by the CEC.

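### NYHA and PGA are carried forward with no exception for death, and only cardiovascular death counts against a subject, so one who dies of another or unknown cause before the 6-month visit can be scored a responder

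*Combined protocol and SAP*

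**What the plan says.** **Endpoint.** The responder class is set at the 6-month MPP follow-up against the MPP enrollment visit (2.1.1). 'Improved' needs better NYHA and neither HF hospitalization nor cardiovascular death. 'Worsened' applies where "HF hospitalization or cardiovascular death has occurred, OR" NYHA is worse. Secondary endpoints 2 and 3 use the same death component. For secondary endpoint 3, an unchanged status "during the MPP follow-up period will be considered a responder to MPP" (2.1.4).

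**Who decides.** Under 2.6 the CEC determines what counts as a cardiovascular death. Under 5.1.1 it is to "classify each death as cardiovascular, vascular, non-cardiovascular/vascular, or unknown". No section says how the last three categories are scored.

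**Missing values.** For the primary endpoint and secondary endpoints 2 and 3, section 2.6.1 states: "The last observation carried forward (LOCF) principle will be utilized for the analysis of NYHA Classification and Patient Global Assessment". It gives unanswered questions as the reason and adds that missing data "affects the number of subjects that can be included in the analysis". Death is not mentioned.

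**Population.** Table 3 states: "Fully enrolled subjects will be included in the analysis population for the study objectives". Section 2.6.2 specifies intention-to-treat "utilizing all available data from fully enrolled subjects".

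**Death and visits.** Section 3.4.3 states: "In case of subject death, the date of study termination is the date of death". NYHA and PGA are collected at the 3-month MPP visit (3.3.6), so a later value than enrollment exists to be carried forward.

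**The concern.** Taken together, these rules let a subject who died before the 6-month assessment count as a success at that assessment. In a single-arm study judged against a 3% performance goal, a handful of responders decides the result, and each wrongly scored subject pushes in the favourable direction.

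The plan leaves open whether such a death is carried forward, excluded or counted as non-response. If this is not settled beforehand, it will be settled once the deaths and the responder count are known, in an open study with no control arm. The omission stands out because 2.6 does say, for secondary endpoint 1, how every CEC category of relation to MPP is counted, including unknown. Nothing equivalent exists for deaths.

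**Working it through.** **1. The plan's own figure.** Inputs: goal 3%, expected rate 10%, one-sided alpha 0.025, power 80% (2.3.1.1); exact lower bound above 3% (2.6). With X binomial, n = 90 and success at X ≥ 7:
- P(X ≥ 7 | 3%) = 0.0188
- P(X ≥ 7 | 10%) = 0.8075

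The smallest n with exact power of at least 80% is 90, as the plan states. Enrollment in 2.5 is 90 / (1 − 0.10) = 100.

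**2. Tracing one subject.** NYHA is better at the 3-month MPP visit, there is no HF hospitalization, and the subject dies before the 6-month visit of a cause that the CEC classes as unknown.
- Analysed? Yes, as fully enrolled (Table 3, 2.6.2).
- 6-month NYHA? None, because participation ended at death (3.4.3). Under 2.6.1 the 3-month value is carried forward.
- Cardiovascular death or HF hospitalization? No.
- Result: every written condition for 'Improved' is met.

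For secondary endpoint 3, unchanged NYHA is enough. Even a death before the 3-month visit could carry the enrollment NYHA forward as 'Unchanged', which counts as a response there. A subject with a CEC-classified HF hospitalization during MPP follow-up would still be 'Worsened'.

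**3. What one subject does to the primary test.** The exact lower bound for x of n is the 0.025 quantile of Beta(x, n − x + 1).

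| n | x | Lower bound | Result |
|---|---|---|---|
| 90 (evaluable target) | 7 | 3.18% | pass |
| 90 | 6 | 2.49% | fail |
| 100 (planned enrollment, all analysed) | 8 | 3.52% | pass |
| 100 | 7 | 2.86% | fail |
| 110 (maximum) | 8 | 3.19% | pass |
| 110 | 7 | 2.60% | fail |

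The minimum passing counts (7, 8, 8) are the same at the final nominal level of 0.0224 in 2.4.

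**4. The three readings at the boundary.** Suppose 90 subjects, seven scored 'Improved', one of whom died as in step 2.
- Carried forward: 7/90, bound 3.18%, pass.
- Excluded: 6/89, bound 2.51%, fail.
- Non-responder: 6/90, bound 2.49%, fail.

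**5. At the expected 10%.** 9/90 less one or two gives 8 or 7, still a pass; less three gives 6, a fail. 10/100 less one or two gives 9 or 8, still a pass; less three gives 7, a fail.

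**6. Likely size.** The documents give no rate for such deaths. Assume that 1% to 5% of subjects die this way after the 3-month visit, and that 10% of them (the planning rate) were improved at 3 months. The expected excess per 90 is 90 × 0.01 × 0.10 = 0.09 to 90 × 0.05 × 0.10 = 0.45 subjects. Added to a true rate of 3%, this raises the chance of at least 7/90 from 0.0188 to between 0.022 and 0.039.

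**7. Secondary endpoints 2 and 3.** They have no stated test. Each affected subject moves the rate by 1/90 = 1.1 points or 1/100 = 1.0 point.

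**The case against.** The best counter-argument is that the plan does not intend to carry values past death. Section 2.6.1 explains missing data by skipped questions and expects it to reduce the number analysed. Section 2.5 enrolls 100 to obtain 90 evaluable, with 10% lost for reasons unrelated to outcome; that allowance would be largely unnecessary if everyone who left were filled in. On this reading a non-cardiovascular death is simply not evaluable and nobody who died is a success. This has force and rules out saying that the plan definitely scores such subjects as improved. It does not close the gap: no section states the exclusion, and it conflicts with Table 3 and 2.6.2.

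The CEC charter (5.1) may group vascular with cardiovascular deaths. It is described as covering adverse event adjudication, so it would not necessarily settle responder scoring.

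Four stronger readings are tempting but not supported:
- *The early stop could turn on such a subject.* Section 2.4 counts subjects who have completed participation, and 3.4.2.6 ties completion to the 6-month MPP visit. A subject who died is probably not among the 45.
- *FDA must agree the rule.* The study is FDA-required, but no section says this.
- *A PGA answer of better at enrollment, carried past death, inflates secondary endpoint 2.* It can, but the cause is mainly that the PGA asks about change since before CRT, which affects living subjects equally. That is a separate issue.
- *The false-positive risk could exceed 20%.* Reaching 2.25 extra subjects per 90 and a probability of 0.226 needs 5% such deaths with half of them improved at 3 months, five times the planning rate.

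**Conclusion.** The concern holds as an ambiguity with one harmful reading. Applied literally, the rules can score a subject who died before the endpoint visit as 'Improved' in the primary endpoint, or as a responder in secondary endpoint 3. Sections 2.5 and 2.6.1 allow another reading, and the plan does not choose.

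The practical effect is probably very small. Section 3.1.4 excludes subjects with life expectancy under 12 months or another life-threatening illness, and follow-up ends about 12 months after implant. The primary conclusion changes only if the count sits exactly at the boundary. The sample size of 90 is unaffected. Confidence is moderate, because the size rests on an assumed death rate. It is still worth correcting, since a primary endpoint should not leave open how a death before the assessment is scored.

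**What to change.** State in 2.6.1, before outcome data are analysed:
- NYHA and PGA are not carried forward past death.
- A subject who dies before the 6-month MPP visit stays in the denominator and is not a responder in the primary endpoint or in secondary endpoints 2 and 3, whatever the CEC death category.

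The 'Worsened' definition can stay tied to cardiovascular death. Add a sensitivity analysis that excludes deaths not classed as cardiovascular, so that the effect of the choice is visible.

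The cost is low. No new data are needed, because the CEC already reviews all deaths in the sub-study (3.4.2.3, 5.1.1). The drawbacks are slightly less favourable rates and that a death unrelated to the heart counts as non-response; the sensitivity analysis addresses the second.

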6. ADVERSE EVENTS

In the course of the clinical investigation, undesired medical events can occur in participating subjects, which are called adverse events (AEs). All AEs shall be assessed by the investigator and shall be documented and reported throughout the clinical investigation.

The investigator shall submit to the sponsor all reportable events using the respective eCRFs provided within the EDC system.

Based on literature research, the adverse events listed in Appendix B may possibly occur as medical complications of a cardiac rhythm management system implant.

6.1 Definitions

6.1.1 Definition of Adverse Event

An AE is defined as any untoward medical occurrence, unintended disease or injury, or untoward clinical signs (including abnormal laboratory findings) in subjects, users or other persons whether or not related to the medical device. This includes:

- Events related to the medical device or the comparator
- Events related to the procedures involved
- For users or other persons, this definition is restricted to events related to the medical devices.

6.1.2 Definition of Adverse Device Effect

An adverse device effect (ADE) is an AE that is related to the use of a medical device. This includes any AE resulting from insufficient or inadequate instructions for use or the deployment, implantation, installation, or operation, or any malfunctioning of a device and any event resulting from use error or from unintentional misuse of the device.

Adverse events, which result from the required medical procedures involved, when implanting, using or testing the respective device, even if not directly related to the device (e.g. anesthetic complications, wound healing disturbances, lead perforation, etc.) are considered ADEs.

Three categories for classification of relationship to the device and/or procedure are available:

- Clearly not related: A relationship of the AE to the device and / or procedure can be excluded.
- Possibly related: It cannot be excluded that there is a connection with the device under investigation and / or the procedure.
- Clearly related: A relationship of the AE to the device and/or procedure is likely/sure.

6.1.3 Serious AEs, ADEs

AEs and ADEs are classified as serious if one or more of the following consequences are fulfilled:

- led to death
- led to serious deterioration in the health of the subject, that either resulted in
 - a life-threatening illness or injury, or
 - a permanent impairment of a body structure or a body function, or
 - in-patient or prolonged hospitalization, or
 - medical or surgical intervention to prevent life-threatening illness or injury or permanent impairment to a body structure or a body function.
- led to fetal distress, fetal death or a congenital abnormality or birth defect.

Note: Planned hospitalization for a pre-existing condition, or a procedure required by the protocol, without serious deterioration in health, is not considered a serious adverse event.

In-patient hospitalization is defined as at least one overnight stay (change of date) in a hospital. Events for which subjects are hospitalized for less than 24 hours without change of date will not be documented as serious, unless one or more of the other seriousness criteria are fulfilled.

6.1.4 Definition of Heart Failure Hospitalization

Hospitalization for worsening heart failure is defined as a hospitalization that includes increased signs and/or symptoms of worsening heart failure requiring the administration or augmentation of intravenous or oral heart failure therapy (e.g., inotropes, diuretics, and/or vasodilators).

A hospitalization classification will be based on the primary admission diagnosis, not on the development of new events that occur during the hospitalization.

For each hospital admission, the investigator will be requested to state whether or not the subject experienced worsening heart failure at the time of admission or during the admission, and if so, whether or not this was the primary reason for admission or secondary to an obvious precipitating factor such as atrial fibrillation. The investigator will also be asked to state whether or not the subject received an intravenous medication for heart failure including diuretics, vasodilators or inotropic agents or a substantial increase in oral diuretic therapy for heart failure.

6.2 Reporting Adverse Events

The investigator has to record any reportable adverse event which occurs during study duration. The adverse event will be classified according to the seriousness, the relation to the implanted devices, and to the procedure. The investigator shall

report to the sponsor, by completing the appropriate eCRF, the following types of events:

- all adverse events related to or possibly related to the implanted system
- any major adverse events related to procedures involved with implanting, using, or testing the implanted system (examples are provided in Section 6.3.1 and definitions are provided in Appendix A: Definition of Terms)
- any adverse device effects, regardless of severity
- any cardiovascular hospitalizations and any other hospitalizations in which cardiovascular symptoms occur during participation in the MPP sub-study (Section 6.3.2 provides definitions)
- most recent heart failure hospitalization that occurs after eligible system implant and before MPP sub-study enrollment (if subject participates in the MPP sub-study; Section 6.1.4 provides definition)
- all adverse events that require additional invasive intervention to resolve, specifically related to the MPP feature of the CRT-D that occur during participation in the MPP sub-study (examples are provided in Section 6.3.3)

Events will be reported on an Adverse Event eCRF. Events should be reported as information is available, even if this results in an incomplete eCRF. The investigator must follow-up all ongoing reportable events either as long as the subject participates in the clinical investigation, the clinical investigation is terminated, or until the event has been resolved, whatever comes first.

The investigator must characterize each event by a single primary diagnosis. The primary diagnosis may describe an event consisting of several clinically recognizable features, symptoms or secondary diagnoses. Note: The observed symptoms and secondary diagnoses must be properly documented in the respective eCRF.

Multiple events may occur simultaneously in one subject. For each medically independent event with a primary diagnosis an individual report must be provided.

In addition, the action taken/treatment should also be provided with any supportive documentation available.

The investigator has to ensure that all relevant information is available. This also includes information from other parties (family, other hospitals, etc.).

If a patient dies during the clinical investigation, the investigator shall document the cause of death, circumstances and place of death (as defined in Section 3.4.2.3). All actions taken, which were initiated to gain further information must be documented in writing and provided to BIOTRONIK, Inc.

Investigators are required to adhere to applicable regulations and reviewing IRB reporting requirements for adverse events.

